### ***2.7 Entinostat Clinical Experience***

Entinostat, also known as MS-275, is a synthetic benzamide derivative that has been demonstrated to preferentially inhibit class I HDACs, especially HDAC type 1. Preclinical animal models of entinostat demonstrated a  $T_{max}$  of 30-40 minutes and  $T_{1/2}$  of one hour. Based on this data, the initial phase I trial of entinostat started dosage at 2 mg/m^2 daily for the first 28 days of a 42 day cycle. Both patients on this daily protocol experienced dose-limiting toxicity during the first cycle, and pharmacokinetic data suggested a half-life of 30-50 times longer than that observed in the animal models. As a result, dosing was changed to biweekly, and all subsequent phase I trials used either weekly or biweekly dosing strategies. Plasma clearance of entinostat in humans follows bi-exponential kinetics suggestive of enterohepatic circulation with a  $T_{1/2}$  of approximately 50 hours. Pharmacodynamic studies have used measurement of histone H3 acetylation in peripheral-blood mononuclear cells (PMBCs) as a surrogate for HDAC inhibition, although this does not nearly reflect the full spectrum of HDAC inhibitor activity. Western blot and flow cytometric assays of this using entinostat demonstrated significant interpatient variability in both magnitude and timing of H3 hyperacetylation but no clear dose-dependence.

The most common side effects observed in the initial phase I study were fatigue (100%), nausea (83%), anorexia (56%), myelosuppression (neutropenia 74%, thrombocytopenia 61%, anemia 26%), headache (52%), hypoalbuminemia (48%), and electrolyte abnormalities (hypocalcemia 43%, hyponatremia 35%, hypophosphatemia 26%). The

most frequent grade 3 toxicities in the 23 patients were nausea (4), hypophosphatemia (4), fatigue (3), diarrhea (3), and neutropenia (3). The only grade 4 event was leukopenia and neutropenia in a single patient. The MTD in this study was 10 mg/m^2 every 2 weeks.

Additional phase I studies have explored alternative dosing schedules without clear definition of an optimal regimen. A dose of 2 mg/m^2 twice weekly was excessively toxic and discontinued in favor of weekly or biweekly dosing in a phase I trial in patients with solid tumors and lymphoma. All subsequent studies have of entinostat have used weekly or biweekly dosing. In a phase I trial in patients with refractory leukemia, 8 mg/m^2 weekly for the first 4 weeks of a 6-week cycle was determined to be the MTD In a phase I trial in patients with refractory solid tumors, the MTD was 6 mg/m^2 weekly for the first 4 weeks of a 6-week cycle. Later phase II trials used fixed dose instead of weight-based dosing of entinostat, with a range of doses and weekly or biweekly scheduling. Most recently, a phase I trial of entinostat in combination with sorafenib in solid tumors demonstrated tolerability of standard full doses of sorafenib (400mg twice daily) with entinostat 10 mg every 2 weeks. The toxicity profile in this trial was similar to that of the initial phase I study, with few events of grade 3 or higher. Therefore the combination with regorafenib, an almost identical VEGF-R2 inhibitor, is expected to be tolerable.

### ***2.8 Rationale for Clinical Trial***

In summary, previous studies have indicated that autophagy may be a mechanism of resistance to both antiangiogenic and cytotoxic drugs. Multiple phase I trials have shown that HCQ is well-tolerated with multiple forms of chemotherapy, and specifically with the combination of FOLFOX/bevacizumab in colorectal cancer, as well as with sorafenib. Based on very striking (Table 1) preclinical data that support the further addition of HDAC inhibition, this trial is proposed as a test of principle that augmented autophagy inhibition can render a purely antiangiogenic therapy more effective. Since regorafenib alone is associated with a 1% response rate, we would view a 15% response rate with the combination as promising and worth developing further.

### 3.0 ELIGIBILITY

#### 3.1 Inclusion Criteria

- 3.1.1 Histologic or cytologic confirmation of metastatic colorectal cancer
- 3.1.2 Measurable disease based on modified RECIST 1.1 criteria
- 3.1.3 Patients should have received adequate therapy with prior 5-fluorouracil, oxaliplatin, and irinotecan, unless contra-indicated, not tolerated or declined.
- 3.1.4 No prior therapy with regorafenib or other anti-angiogenic tyrosine kinase inhibitor
- 3.1.5 No prior or current therapy with an HDAC inhibitor
- 3.1.6 Age 18 years or older
- 3.1.7 ECOG performance status of 0 or 1
- 3.1.8 If a female of childbearing potential, has a negative serum blood pregnancy test during screening and a negative urine pregnancy test within 3 days prior to receiving the first dose of study drug. If the screening serum test is done within 3 days prior to receiving the first dose of study drug, a urine test is not required. If a patient is of childbearing potential the patient must agree to use effective contraception (see Appendix C for acceptable methods) during the study and for 120 days after the last dose of study drug. Non-childbearing potential is defined as (by other than medical reasons):
  - $\geq 45$  years of age and has not had menses for  $>2$  years
  - Amenorrheic for  $<2$  years without a hysterectomy and oophorectomy and a follicle-stimulating hormone value in the postmenopausal range upon pre-study (screening) evaluation
  - Post hysterectomy, oophorectomy or tubal ligation. Documented hysterectomy or oophorectomy must be confirmed with medical records of the actual procedure or confirmed by an ultrasound. Tubal ligation must be confirmed with medical records of the actual procedure otherwise the patient must be willing to use 2 adequate barrier methods throughout the study, starting with the screening visit through 120 days after the last dose of study drug

- 3.1.9 If male, agrees to use an adequate method of contraception (see Appendix C) starting with the first dose of study drug through 120 days after the last dose of study drug
- 3.1.10 Life expectancy of greater than 3 months
- 3.1.11 Patients must have the ability to understand and the willingness to sign a written informed consent document.
- 3.1.12 Adequate bone-marrow, liver, and renal function as assessed by the following laboratory requirements within 4 weeks of starting treatment
- Absolute neutrophil count  $\geq 1,500$  per uL
  - Hemoglobin  $\geq 9$  g/dL
  - Platelets  $\geq 100,000$  per uL
  - Creatinine  $\leq 1.5$  x ULN **OR** Creatinine clearance (CrCl)  $\geq 60$  by Cockcroft-Gault Equation if Creatinine  $> 1.5$
  - AST and ALT  $\leq 2.5$  x ULN ( $\leq 5$  x ULN if documented liver metastases)
  - Total bilirubin  $\leq 1.5$  ULN **OR** direct bilirubin  $\leq$  ULN if total bilirubin  $> 1.5$  x ULN
  - INR  $\leq 2.0$
- 3.1.13 Experienced resolution of toxic effect(s) of the most recent prior anti-cancer therapy to Grade  $< 1$  (except alopecia or neuropathy). If patient underwent major surgery or radiation therapy of  $> 30$  Gy, they must have recovered from the toxicity and/or complications from the intervention.

### ***3.2 Exclusion Criteria***

- 3.2.1 History or current evidence of any condition, therapy, or laboratory abnormality that might confound the results of the study, interfere with the patient's participation for the full duration of the study, or is not in the best interest of the patient to participate, in the opinion of the treating Investigator, including, but not limited to:
- a) Myocardial infarction or arterial thromboembolic events within 6 months prior to screening or severe or unstable angina, New York Heart Association (NYHA) Class III or IV disease, or a QTc interval  $> 470$  msec.
  - b) Uncontrolled hypertension or diabetes mellitus.
  - c) Another known malignancy that is progressing or requires active treatment.

- d) Any prior history of other cancer within the prior 5 years with the exception of adequately treated basal cell carcinoma or cervical intraepithelial neoplasia [CIN]/cervical carcinoma in situ or melanoma in situ).
  - e) Active infection requiring systemic therapy
  - f) Known active central nervous system (CNS) metastases and/or carcinomatous meningitis.
- 3.2.2 Any contraindication to oral agents or significant nausea and vomiting, malabsorption, or significant small bowel resection that, in the opinion of the investigator, would preclude adequate absorption.
- 3.2.3 Allergy to benzamide, inactive components of entinostat, or any of the other administered therapies
- 3.2.4 Known psychiatric or substance abuse disorders that would interfere with cooperation with the requirements of the study.
- 3.2.5 Currently participating and receiving study therapy or has participated in a study of an investigational agent and received study therapy or used an investigational device within 4 weeks of the first dose of study drug.
- 3.2.6 If female, is pregnant or breastfeeding.
- 3.2.7 Known G6PD deficiency, severe psoriasis, porphyria, macular degeneration, or severe diabetic retinopathy due to greater potential HCQ toxicity
- 3.2.8 Patients with pre-existing hypertension should be on a stable antihypertensive regimen and have a blood pressure  $\leq 150/100$  mmHg at the time of enrollment.
- 3.2.9 Evidence or history of bleeding diathesis. Any hemorrhage or bleeding event of CTCAE grade 3 or higher within 4 weeks of start of study medication
- 3.2.10 Non-healing wound, ulcer, or bone fracture
- 3.2.11 Patients using warfarin are excluded. Patients using other oral or parenteral anticoagulation are not excluded provided they are on a stable dose of anticoagulant but must undergo more frequent platelet count monitoring (see section 4.8).

## 4.0 TREATMENT PLAN

**Table 2: Dosing Schedule**

Drug	Dose	Route	Schedule
Regorafenib	160 mg daily	Oral	Daily for 21 days of each 28-day cycle
Entinostat	2-5 mg weekly	Oral	Days 1, 8, 15, and 22 of each 28-day cycle
Hydroxychloroquine	400-1200 mg daily	Oral	Days 1-28 of each 28-day cycle

### ***4.1 Regorafenib Dosing***

All patients will receive regorafenib at the FDA-approved dose of 160 mg by mouth daily for days 1-21 of a 28-day cycle. As noted below, dose decreases of regorafenib are often required in the initial cycle, followed by tolerance of full doses in subsequent cycles: such manipulations of the regorafenib dose are standard, and will not be taken into account in determining the MTD. Should excess toxicity attributable to regorafenib be repeatedly observed, the principal investigator may institute a standard initial dose escalation period. This will consist of regorafenib 80mg daily for the first 7 days of therapy, followed by increase to 120 mg for days 8-14 if 80mg tolerated, and 160 mg for days 15 and beyond if 120 mg tolerated.

### ***4.2 Phase I Dose Escalation of Hydroxychloroquine and Entinostat***

We expect that the full doses of each drug will be well-tolerated based on previous studies. Patients will begin treatment with weekly oral entinostat and daily oral HCQ given in divided doses, per Table 3 below. The starting phase I total daily dose for HCQ is 600 mg, based on our previous Phase I trials. Weekly dosing of entinostat has been established as the best balance between toxicity due to accumulation and drug pharmacodynamics. Entinostat is currently undergoing study at a dose of 5mg weekly in a phase III trial in breast cancer, and 5mg weekly will be the target dose for this study. Given the potential for overlapping toxicities in this combination, an initial dose of 3 mg will be used, with subsequent escalation.

Three patients will be treated at the starting doses, with escalation to an entinostat dose of 5mg at dose level 2 followed by dose escalation of HCQ to 1200 mg/daily at dose level 3, with expansion to a total of 6 patients once safety has been established. Dose levels 2A and 2B will not be used during the dose escalation phase, they will be used only if de-escalation from dose level 3 is required. Toxicity attributable to hydroxychloroquine is not expected given its excellent tolerability in multiple phase II studies with combination chemotherapy using 1200 mg per day. In the event that dose level 3 exceeds the MTD (as described below), provision is made for stepwise dose de-escalation by 200 mg to dose levels 2B (1000 mg total daily dose HCQ) then 2A (800 mg total daily dose HCQ).

Before accrual to the next dose level may begin, all patients in the first cohort must complete the first 4 weeks of treatment, permitting toxicities to be assessed. The target DLT rate is  $\leq 33\%$ . The MTD will be defined as a) the dose producing DLT in 1 out of 6 patients, or b) the dose level below the dose which produced DLT in  $\geq 2$  out of 3 patients, or in  $\geq 2$  out of 6 patients. The rules for dose escalation and cohort size are outlined in Table 3. No intra-patient dose escalation is planned.

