### ***4.3 Phase II Dose Expansion***

To determine the recommended phase II dose (RP2D), at least 6 patients must be treated at the MTD for 2 cycles. In order to fulfill this criterion, patients who go off study before the completion of 2 cycles for reasons other than toxicity (e.g. disease progression) will be replaced in this cohort. The RP2D will be defined as a dose in which fewer than 33% of patients have a DLT and at which chronic administration is tolerated. To evaluate for chronic toxicity, tolerability is defined as 4 out of 6 patients treated for 2 cycles at the RP2D receiving during cycle 2:

- 1) At least 80% (in total mg per cycle) of the regorafenib dose at which the patient begins cycle 2
- 2) At least 75% of entinostat doses, with no more than one dose reduction
- 3) At least 80% (in total mg per cycle) of the HCQ doses

Should chronic tolerability fail to be demonstrated at the initial RP2D, the previous dose level (or a lower dose level at the discretion of the principal investigator) will be expanded until at least 6 patients have been treated at this new RP2D for 2 cycles. Evaluation for chronic tolerability will be performed as above after 2 cycles until the RP2D is determined.

After determination of the RP2D, an additional 20 patients will be enrolled at this dose level in the Phase II portion.

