#### ***4.5 DLT Definition and Escalation Decision Process***

Dose Limiting Toxicities will be defined by toxicity occurring during the first 4 weeks of this study. Any non-hematologic AE of Grade 3 or higher that is judged to be probably treatment-related will be considered a DLT with the exceptions of fatigue; rash attributable to regorafenib; or nausea, vomiting, or diarrhea that has improved to Grade < 1 within 72 hours. Any non-hematologic AE of Grade 4 or higher of any duration that is judged to be probably treatment-related will be considered a DLT except for elevations of lipase and/or amylase in the absence of clinical pancreatitis.

The following hematologic DLT will be considered if any occurs in the first cycle:

- 1) grade 4 neutropenia lasting more than 7 days
- 2) febrile neutropenia (T > 100.4 F in presence of ANC <500)
- 3) platelet count less than 25,000/mm^3
- 4) platelet count less than 50,000/mm^3 with clinically significant hemorrhage

If a DLT is observed in exactly 1 patient in the first cohort of 3, the cohort will be expanded to 6. If a DLT occurs in 2 or more patients per cohort, then the cohort one dose below will be the declared the MTD provided that at least 6 patients have been treated at that level with fewer than one third having DLTs. The rules for dose escalation and cohort size are outlined in Table 3. No intra-patient dose escalation is planned.

***Evaluable Patients:*** Patients will be evaluable for toxicity if they have taken one dose of HCQ and entinostat. Patients who experience a dose-limiting toxicity will be evaluable for the cohort after at least one dose of HCQ and one dose of entinostat. To be considered for evaluability in a Phase I cohort in the absence of dose-limiting toxicity, patients should have completed  $\geq 85\%$  of HCQ doses, and at least 3 of 4 entinostat doses. Phase II patients will be evaluable for response if they have completed 85% of their expected dose of HCQ and at least 3 doses of entinostat in the initial 4 weeks, in the absence of progression. Patients who do not meet these criteria will be replaced. In the unexpected event of excess toxicity at dose level 1, there is provision (Table 3) for a dose reduction of both HCQ and entinostat.

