## 7.0 STATISTICS

### 7.1 Primary Endpoints

#### 7.1.1 Phase I

The Phase I methodology will be a standard Phase I escalating trial with three patients per level, expanding to six patients per level in the event of dose-limiting toxicity at any level, and provision for expansion to 20 additional patients at the recommended Phase II dose to better characterize the optimal dose and the variation in toxicity at that level. A minimum of 4 weeks of combination therapy with hydroxychloroquine, entinostat, and regorafenib are required in the third patient before escalation to the next dose is initiated. At the MTD, at least 6 patients must be treated for 2 cycles to evaluate chronic toxicity and determine the RP2D (see section 4.3 for details).

We will calculate the percentage of subjects with toxicities at each dose level. We expect that doses close to full single agent doses will be tolerable. Three patients will be initially treated at each dose level. The plan for escalation is described below:

Three patients will initially be treated at each dose level.

If 0/3 patients experience DLT, then the dose will be escalated.

If 2-3/3 patients experience DLT, then the MTD has been exceeded. Three additional patients are treated at the previous dose (if only 3 had been treated) as a total of 6 patients must be treated at the MTD.

If 1/3 patients experience DLT, then 3 additional patients are treated. If none of the additional patients develop DLT, then the dose will be escalated, otherwise escalation ceases and the previous dose will be expanded to a total of 6 patients.

To assure safety in this phase I study, the operating characteristics of the escalation rule to be employed have been determined. The operating characteristics denote the probability of escalation to the next dose level, for a given true DLT rate. For a true DLT that is high, we desire the probability of escalation to be low. As noted in the table, the probability of escalating beyond a certain dose level, if that dose level truly has a 10% DLT rate, is 0.91. On the other hand, if the true DLT rate is 40%, there is only a 31% chance of dose escalation.

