### 7.3 *Sample Size/Accrual Rate*

Phase I: The phase I study will involve six possible dose levels, although accrual at more than 3 or 4 levels is very unlikely. The total sample size will range from a minimum of 12 to a maximum of 24 patients. We expect accrual to be completed within 6-9 months.

Phase II: During the Phase II portion we will enroll up to 20 additional patients and expect an accrual time of approximately 1 year.

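### The MTD definition in 4.2(a) lacks the qualifier highest and so clashes with the rules that escalate at 1/6, and 7.1.1 and 4.3 leave open which dose follows a failed level 3

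*Combined protocol and SAP*

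**What the plan says.** **MTD definition.** Section 4.2 gives two limbs. Limb (a) is "The MTD will be defined as a) the dose producing DLT in 1 out of 6 patients". Limb (b) takes the level below one with at least 2/3 or at least 2/6 DLTs.

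**Escalation rule.** Table 4 escalates at 1/6. Section 7.1.1 does the same after one DLT in the first three patients: "If none of the additional patients develop DLT, then the dose will be escalated, otherwise escalation ceases and the previous dose will be expanded" to six patients. Section 4.5 declares the dose below a failed cohort the MTD "provided that at least 6 patients have been treated at that level with fewer than one third having DLTs".

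**After level 3 fails.** Section 4.2 says of levels 2A and 2B that "they will be used only if de-escalation from dose level 3 is required", and that "provision is made for stepwise dose de-escalation by 200 mg to dose levels 2B" and then 2A. Table 3 lists the levels in the order -1, 1, 2, 2A, 2B, 3. Section 7.1.1 never mentions 2A or 2B. For a level with two or three DLTs in three patients it says "Three additional patients are treated at the previous dose (if only 3 had been treated" there). If level 3 passes on DLTs but is not tolerated over two cycles, 4.3 says that "the previous dose level (or a lower dose level at the discretion of the principal investigator) will be expanded".

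**Size.** Section 7.3 states: "The phase I study will involve six possible dose levels, although accrual at more than 3 or 4 levels is very unlikely". It gives a Phase I range of 12 to 24 patients. The synopsis gives 32 to 44 in total, which is that range plus the 20 Phase II patients.

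**The concern.** The MTD is the main Phase I result and the starting point for the RP2D, at which 20 more patients are treated. Two sets of instructions can turn the same DLT data into different MTDs.

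The first is 4.2(a). While escalation is still open, a level with 1/6 is the MTD under the definition and a level to be passed under Table 4 and 7.1.1. Limbs (a) and (b) also both miss 0/6 at level 3, although 4.2 expects full doses to be well tolerated. At a true DLT rate of 10%, six patients without a DLT have probability 0.9^6 = .53.

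The second is the step after a failed level 3. The choice is between HCQ 1000 or 800 mg (2B, 2A) and 600 mg (level 2). Section 2.6 reports that 600 mg daily inhibited autophagy incompletely in an earlier CNS consortium trial, so skipping two planned levels would matter to the trial's own rationale.

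**Working it through.** **1. Which rule Table 11 assumes.** Let p be the true DLT rate at a level and q = 1 - p. If 1/6 escalates, a level is passed with 0/3, or with 1/3 followed by 0/3:

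P(escalate) = q^3 + 3p·q^2·q^3 = q^3 + 3p·q^5

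| p | .1 | .2 | .3 | .4 | .5 | .6 | .7 | .8 |
|---|---|---|---|---|---|---|---|---|
| Table 11 | .91 | .71 | .49 | .31 | .17 | .08 | .03 | .01 |
| q^3 + 3p·q^5 | .906 | .709 | .494 | .309 | .172 | .082 | .032 | .009 |
| q^3 only (1/6 stops) | .729 | .512 | .343 | .216 | .125 | .064 | .027 | .008 |

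All eight entries match the rule that escalates at 1/6. The rule that stops at 1/6 does not fit, for example .729 against .91 at p = .1. So Table 11 agrees with Table 4 and 7.1.1, and 4.2(a) is the text to correct. The difference between the last two rows is how often a level ends at 1/6 by this route: 17.7%, 19.7%, 15.1% and 9.3% at p = .1 to .4. That shows how often the texts part at one level. It does not predict conduct.

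**2. Where 7.1.1 points after level 3 fails.** It adds three patients at the previous dose if that dose has had only three. Levels 2A and 2B are not used in escalation, so they hold no patients at that moment. The dose with patients is level 2. Section 7.1.1 does not name it, so this is an inference.

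**3. How often this matters.** The protocol gives no DLT rates by level, so these are assumed: equal rates of 5%, 10%, 20% and 30%, and two rising patterns for levels -1/1/2/2A/2B/3:
- A: .05/.05/.10/.125/.15/.20
- B: .05/.10/.15/.20/.25/.30

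Patients are taken as independent, and level 3 is filled to six. A filled level fails with two or more DLTs:

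f(p) = 1 - (q^6 + 6p·q^5)

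P(level 3 opens and fails) = P(escalate, level 1) × P(escalate, level 2) × f(p at level 3)

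Worked example at 10%: .906 × .906 × .114 = .094.

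Once level 3 has failed, the 4.2 path and the literal 7.1.1 path end at different doses unless 2B and 2A both fail:

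P(MTD differs, given failure) = 1 - f(2B) × f(2A)

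Worked example for pattern B: 1 - .466 × .345 = .839.

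| Assumed rates | Level 3 opens and fails | MTD differs, given that | P(N > 24) on the 4.2 path |
|---|---|---|---|
| 5% | .031 | .999 | .0002 |
| 10% | .094 | .987 | .003 |
| 20% | .173 | .881 | .020 |
| 30% | .142 | .664 | .029 |
| A | .304 | .963 | .014 |
| B | .428 | .839 | .051 |

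If level 3 were left at three patients after 0/3, the first column would be .025, .077, .146, .124, .257 and .373.

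**4. Phase I size.** The last column is an exact enumeration of the DLT decisions, with level 3 followed on failure by 2B, 2A, 2, 1 and -1. On that path all six levels can be filled, so the limit is 6 × 6 = 36 before replacements. On the literal 7.1.1 path only four levels can be used, and 4 × 6 = 24, the maximum in 7.3. The enumeration omits the two-cycle step in 4.3, which can add patients.

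**The case against.** The case for leaving the text alone is a good one. Limb (a) is a definition, and many readers will take it as the usual 3+3 shorthand for the highest dose with at most 1/6. The operative rules in Table 4 and 7.1.1 agree with each other and with Table 11. On de-escalation, 4.2 is the specific text, Table 3 puts 2B directly below level 3, and 7.3 counts six levels. Section 7.1.1 is a generic 3+3 paragraph that never names level 2, and 4.3 lets the investigator go lower in any case.

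Most of this stands. It shows what is intended and why the point is minor. It does not supply the missing qualifier, cover 0/6 at level 3, or settle what the previous dose means in 7.1.1 and 4.3.

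A reader might infer three stronger things that the documents do not support:
- **That 4.2(a) is right only at level 3.** A level with 1/6 is also the MTD at any lower level once the level above it has failed. The limb misleads only while escalation is open.
- **That 4.5 and Table 4 share the de-escalation gap.** Their references to the dose below read naturally as 2B, given the order in Table 3.
- **That the planned sample size is wrong and must be raised.** Section 7.3 itself says that more than three or four levels is very unlikely, and the enumeration agrees.

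**Conclusion.** Both inconsistencies are in the current text, and both are minor. The conflict in 4.2(a) needs no inference, and 4.2(a) is the text at fault. No effect on the trial's result is claimed for it, because the team would probably apply Table 4.

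The de-escalation conflict depends on an inference about 7.1.1 and is confined to someone following that section over 4.2. The occasion arises in about 3% to 17% of trials at equal rates of 5% to 30%, and in 30% and 43% under the rising patterns. In those trials the MTDs would differ in 66% to over 99%. A reader might take these last figures as the chance of a wrong MTD. They are conditional on level 3 opening, failing, and 7.1.1 being followed literally, and all rest on assumed DLT rates. The RP2D still depends on the two-cycle tolerability step in 4.3.

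The maximum of 24 in 7.3 is not a strict maximum on the 4.2 path, but the DLT rules exceed it in only 0.02% to 5% of trials under these assumptions. Table 11 and the Phase II power stand as they are.

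**What to change.** 1. **Section 4.2:** replace the definition with: *The MTD is the highest dose level at which 6 patients have been treated with at most 1 DLT.* This agrees with the proviso in 4.5 and covers both 0/6 and 1/6 at level 3.
2. **Sections 7.1.1 and 4.3** (and, for clarity, 4.5 and Table 4): state that the order below level 3 is 2B, 2A, then 2, that each is filled to six before it is declared the MTD, and that there is no return to a failed level.
3. **Sections 4.2 and 4.5:** the escalation rules are in Table 4, so correct the citation of Table 3.
4. **Section 7.3 and synopsis:** call 24 and 44 expected upper figures, or make 24 a hard cap. Printing the theoretical limits of 36 and 56 (36 + 20) is optional.

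The cost is amendment wording, with no new procedures. The 2B/2A path is already in 4.2. Compared with following 7.1.1 literally, it averages 0.1 to 1.0 more Phase I patients at equal rates of 5% to 30%, and 1.4 and 2.6 more under patterns A and B. A hard cap would also need a rule for choosing the dose if the cap is reached.
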